9.0 ADVERSE EVENTS

9.1 LEE001 TREATMENT RELATED EVENTS

The following grade 3 and 4 AEs are suspected to be related to LEE011 treatment for reporting purposes:

- Anemia, febrile neutropenia, leukopenia, lymphopenia, neutropenia, thrombocytopenia;
- Electrocardiogram QT prolonged, hypertension;
- Diarrhea, nausea, vomiting, stomatitis, mucositis; abdominal pain;
- Pneumonia
- Asthenia/fatigue; decreased appetite
- Hepatocellular injury; Hepatic function abnormalities (elevated transaminases); elevated creatinine
- Rash;
- Hyponatremia

9.2 CHEMOEMBOLIZATION TREATMENT RELATED EVENTS

The following events are considered to be expected for reporting purposes following chemoembolization:

- Abdominal pain;
- Fever;
- Fatigue;
- Nausea;
- Elevated liver enzymes;
- Infection;
- Cholecystitis;
- Hemorrhage;
- Thromboembolic events;
- Alopecia;
- Hyperpigmentation;
- Mucositis;
- Hepatocellular injury; hepatic function abnormalities (elevated transaminases)

9.3 ADVERSE EVENT MONITORING

Adverse event data collection and reporting, which are required as part of every clinical trial, are done to ensure the safety of subjects enrolled in the studies as well as those who will enroll in future studies using similar agents. Adverse events are reported in a routine manner at scheduled times during a trial. Additionally, certain adverse events must be reported in an expedited manner to allow for optimal monitoring of subject safety and care.

All subjects experiencing an adverse event, regardless of its relationship to study drug, will be monitored until:

- the adverse event resolves or the symptoms or signs that constitute the adverse event return to baseline;
- any abnormal laboratory values have returned to baseline;

- there is a satisfactory explanation other than the study drug for the changes observed; or
- death.

9.3.1 **Definition**

An adverse event is defined as any untoward or unfavorable medical occurrence in a human research study participant, including any abnormal sign (for example, abnormal physical exam or laboratory finding), symptom, clinical event, or disease, temporarily associated with the subject's participation in the research, whether or not it is considered related to the subject's participation in the research.

Adverse events encompass clinical, physical and psychological harms. Adverse events occur most commonly in the context of biomedical research, although on occasion, they can occur in the context of social and behavioral research. Adverse events may be expected or unexpected.

Severity

Adverse events will be graded by a numerical score according to the defined NCI Common Terminology Criteria for Adverse Events (NCI CTCAE) and version number specified in the protocol. Adverse events not specifically defined in the NCI CTCAE will be scored on the Adverse Event log according to the general guidelines provided by the NCI CTCAE and as outlined below.

- Grade 1: Mild;
- Grade 2: Moderate;
- Grade 3: Severe or medically significant but not immediately life threatening;
- Grade 4: Life threatening consequences;
- Grade 5: Death related to the adverse event

Serious Adverse Events

ICH Guideline E2A and the UTSW IRB define serious adverse events as those events, occurring at any dose, which meets any of the following criteria:

- Results in death;
- Immediately life-threatening;
- Results in inpatient hospitalization or prolongation of existing hospitalization;
- Results in persistent or significant disability/incapacity;
- Results in a congenital anomaly/birth defect;
- Based upon appropriate medical judgment, may jeopardize the subject's health and may require medical or surgical intervention to prevent one of the other outcomes listed in this definition.

Note: A "Serious adverse event" is by definition an event that meets any of the above

criteria. Serious adverse events may or may not be related to the research project. A serious adverse event determination does not require the event to be related to the research. That is, both events completely unrelated to the condition under study and events that are expected in the context of the condition under study may be serious adverse events, independent of relatedness to the study itself. As examples, a car accident requiring overnight hospitalization would be a serious adverse event for any research participant; likewise, in a study investigating end-stage cancer care, any hospitalization or death would be a serious adverse event, even if the event observed is a primary clinical endpoint of the study.

Refer to the UTSW IRB website at <http://www.utsouthwestern.net/intranet/research/research-administration/irb/study-management/adverse-events.html> to determine when a serious adverse event requires reporting to the IRB.

9.3.2 Unanticipated Problems:

The term “unanticipated problem” is found, but not defined in the regulations for the Protection of Human Subjects at 45 CFR 46, and the FDA regulations at 21 CFR 56. Guidance from the regulatory agencies considers unanticipated problems to include any incident, experience, or outcome that meets each of the following criteria:

- Unexpected (in terms of nature, severity or frequency);

AND

- Definitely, probably, or possibly related to participation in the research;

AND

- Serious or a possible unexpected problem in that the research places subjects or others at greater risk of harm than was previously known or recognized. Note: Any serious adverse event would always suggest a greater risk of harm.

Follow-up

All adverse events will be followed up according to good medical practices.

9.3.3 Reporting

Local unanticipated problems require expedited reporting, and are submitted to the UTSW IRB through the UTSW eIRB and to the SCC DSMC Coordinator. Hardcopies or electronic versions of the eIRB report; FDA Form #3500A forms, or other sponsor forms, if applicable; and/or any other supporting documentation

available should be forwarded to the DSMC Coordinator. The DSMC Coordinator forwards the information onto the DSMC Chairman who determines if immediate action is required. Follow-up eIRB reports, and all subsequent SAE documentation that is available are also submitted to the DSMC Chair who determines if further action is required. *(See Appendix IV of the SCC DSMC Plan for a template Serious Adverse Event Form which may be utilized when a sponsor form is unavailable and SAE submission to the eIRB is not required).*

All local serious adverse events which occur on research subjects on protocols for which the SCC is the DSMC of record require reporting to the DSMC regardless of whether IRB reporting is required. Hardcopies or electronic versions of the FDA Form #3500A forms, or other sponsor forms, if applicable; and/or any other supporting documentation available should be forwarded to the DSMC Coordinator.

If the event occurs on a multi-institutional clinical trial coordinated by the Cancer Center, the Disease Oriented Team (DOT) Manager or lead coordinator ensures that all participating sites are notified of the event and resulting action, according to FDA guidance for expedited reporting. DSMC Chairperson reviews all serious adverse events within upon receipt from the DSMC Coordinator. The DSMC Chairperson determines whether action is required and either takes action immediately, convenes a special DSMC session (physical or electronic), or defers the action until a regularly scheduled DSMC meeting.

Written reports to:

[name] [name]
c/o
QA Coordinator
[name]
[name]
[contact]
[contact]
Email: [contact]

UTSW SCC Data Safety Monitoring Committee Coordinator
Email: [contact]
[contact] or deliver to BLB.306

UTSW Institutional Review Board (IRB)
Submit via eIRB with a copy of the final sponsor report as attached supporting documentation.

1. SAEs

Local serious adverse events (SAEs) for studies where SCC DSMC is the DSMC of record require reporting to the DSMC coordinator within 2 working days of PI awareness, or as described in the protocol.

2. Unanticipated Problems

Local unanticipated problems require reporting to the UTSW IRB within 2 working days of PI awareness of the event.

Unanticipated problems, including those that occur as non-local events, require reporting to the UTSW IRB within 10 working days of PI awareness of the event.

For further guidance for Investigators regarding safety reporting requirements for INDs and BA/BE studies, refer to FDA Draft Guidance document:

<http://www.fda.gov/downloads/Drugs/GuidanceComplianceRegulatoryInformation/Guidances/UCM227351.pdf>

9.4 STOPPING RULES

There is no interim analysis planned.

Simmons Cancer Center Data and Safety Monitoring Board (DSMB) will oversee this study and will determine if early stoppage of the trial is needed due to unacceptable rates of drug related serious adverse events.

To assess for aggregate severe hepatobiliary toxicity and severe events that occur at any time during the study, if 2 total grade 5 or 2 grade 4 adverse events (lasting ≥ 7 days) occur while at patient is receiving study treatment and the adverse events are attributed to either being definitely, probably, or possible related to the study treatment then the study will terminate with no further patients entered.

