1.5 PROLIFERATION FOLLOWING CHEMOEMBOLIZATION IN HEPATOCELLULAR CARCINOMA

There are multiple pre-clinical and clinical studies suggesting that hepatic artery embolization leads to increased HCC tumoral cell proliferation. Kim et al reported a case series in which explanted livers from transplanted patients undergoing chemoembolization 3 to 4 weeks prior to transplant had an elevated Ki67 proliferative index compared to non-treated controls. The increase in proliferative index within intratumoral endothelial and tumor cells was likely secondary to a post-embolization ischemic necrosis. (14) Farris et al also demonstrated a statistically significant difference in proliferation, again measured by the Ki67 proliferative index, between patients undergoing chemoembolization and control patients. (15)

1.6 CD4/6 INHIBITION AND REDUCTION OF PROLIFERATION IN PRE-CLINICAL HEPATOCELLULAR TUMOR MODELS AND EARLY STAGE CLINICAL TRIALS IN HCC

Our group previously demonstrated that inhibition of CDK4/CDK6 potently suppressed proliferation in HCC tumor models. For example, in a hepatoma xenograft model there was substantial suppression of proliferation following CDK4/6 inhibition (Figure 2). Similarly, in necrotic mouse livers following CCL4 administration, CDK4/6 inhibition had a profound impact on aberrant proliferation (Figure 3). These, and additional preclinical data served as the basis for a small single arm Phase II trial in advanced HCC using the CD4/6 inhibitor, palbociclib. This study used Rb and p16ink4 staining of tumor tissue as inclusion criteria. The immunohistochemical stains were developed and optimized by [name], who assisted in developing this study. This study treated 23 HCC patients who had failed on previous sorafenib therapy due to either intolerance or disease progression with palbociclib. The safety profile was largely consistent with CDK4/6 inhibition, the most common adverse event was bone marrow suppression. Grade 3 and 4 adverse events included the following: thrombocytopenia, 43%; neutropenia, 43%; leucopenia, 30%. (16) There was no evidence of liver related toxicity, including elevated AST and/or or AST and/or total bilirubin, following palbociclib administration in these patients with underlying cirrhosis. ([Littman](#) SJ, Gastrointestinal Cancers Symposium 2015, abstract 277)

[figure not shown]

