6.6 DOSE LIMITING TOXICITIES-PHASE IB COMPONENT

The phase Ib component of the study will consist of 3+3 dose escalation rule with the dose of LEE011 escalating up to 600mg daily to determine the maximum tolerated dose (MTD) that will be used during the phase II component. The dose levels for the phase Ib aspect will be 200 mg, 400 mg, or 600 mg daily.

Only the first cycle of therapy (one cycle equals to one month) will be used to determine dose limiting toxicity (DLT). However, if two total grade 5 adverse events or 2 Grade 4 adverse events (lasting ≥ 7 days); occur at any time while the patient is still receiving study treatment that are either: definitely, probably, or possibly related to either LEE011 or TACE the study will be terminated to enrollment.

Only patients started on the first dose of LEE011 will be included in the evaluation of DLT. If a patient has a DLT that patient will not receive further LEE011. Patients following initial chemoembolization who never receive LEE011 will not be included in the MTD analysis and will be replaced. The patients will be followed for thirty days following the initial chemoembolization for safety assessment. Patients will be enrolled into the next highest drug cohort only after 3 or 6 patients have completed the first cycle of therapy. Once the MTD is determined, patients at the MTD dose will continue with LEE011 and represent the first three patients accrued to the phase II aspect.

Due to observed (TACE related, non DLT) toxicity on cohort 1 specific criteria for cohort 1 has been developed after discussion with the FDA. Cohort 1 has been expanded to 6 patients. Decision for dose escalation will be made using the following criteria:

- No or one DLT: the next three patients will be assigned to next higher dose level (400 mg of LEE011).
- At least two toxicities: the MTD is exceeded and the phase I component of the trial will be stopped with no continuation into the phase II component.

For Cohort 2 and 3 the following traditional 3+3 dose escalation rules will be used:

- If a dose limiting toxicity (DLT) is observed in 1 out of 3 patients at a given dose level, up to 3 additional patients will be enrolled and treated at that dose level.
- If 2 out of 3-6 patients at that dose level have DLTs, the dose will be decreased to the previous dose level, and up to 3 additional patients will be enrolled at that dose level for a total of 6 patients.

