16.0 DATA AND SAFETY MONITORING PLAN

Trial monitoring will be conducted no less than annually and refers to a regular interval review of trial related activity and documentation performed by the DOT, which includes but is not limited to accuracy of case report forms, protocol compliance, timeliness and accuracy of Velos entries and AE/SAE management and reporting. Documentation of trial monitoring will be maintained along with other protocol related documents and will be reviewed during internal audit.

Study PI or designated Co-investigator and the research coordinator will attend the weekly Phase I research meeting during the dose escalation phase. Toxicity and dose escalation reviews will be performed in real-time by the Phase I DOT and DSMC. As the study transitions to the Phase II stage, toxicity will be reviewed at the GI DOT research meetings and by DSMC. These reviews will be documented by distributing reports of the findings to the members of the GI DOT and investigators.

The UTSW Simmons Cancer Center (SCC) Data Safety Monitoring Committee (DSMC) is responsible for monitoring data quality and patient safety for all UTSW SCC clinical trials. As part of that responsibility, the DSMC reviews all local serious adverse events and unanticipated problems in real time as they are reported and reviews adverse events on a quarterly basis. The quality assurance activity for the Clinical Research Office provides for periodic auditing of clinical research documents to ensure data integrity and regulatory compliance. A copy of the DSMC plan is available upon request.

The SCC DSMC meets quarterly and conducts annual comprehensive reviews of ongoing clinical trials, for which it serves as the DSMC of record. The QAC works as part of the DSMC to conduct regular audits based on the level of risk. Audit findings are reviewed at the next available DSMC meeting. In this way, frequency of DSMC monitoring is dependent upon the level of risk. Risk level is determined by the DSMC Chairman and a number of factors such as the phase of the study; the type of investigational agent, device or intervention being studied; and monitoring required to ensure the safety of study subjects based on the associated risks of the study. Protocol-specific DSMC plans must be consistent with these principles. Safety is monitored in real-time as serious adverse events and adverse events, which are unanticipated problems, are submitted to the DSMC and IRB with attributions.

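### The mandatory stopping rule counts grade 5 and prolonged grade 4 events separately, so a related death plus one prolonged grade 4 event does not close enrolment, although two prolonged grade 4 events do

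*Combined protocol and SAP*

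**What the plan says.** The rule appears twice. Section 9.4 closes the study to further entry "if 2 total grade 5 or 2 grade 4 adverse events" occur, and section 6.6 ends enrolment "if two total grade 5 adverse events or 2 Grade 4 adverse events" occur. In both places the grade 4 events must last at least 7 days, the patient must still be on study treatment, and the attribution must be at least possible. Section 6.6 names LEE011 or TACE. Section 9.4 refers to study treatment, which section 6.2 defines as the combination. The opening clause of the rule in 9.4 gives its purpose as judging severe toxicity in aggregate, at any time in the study.

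The sentence before the rule gives a separate, discretionary route: the DSMB "will determine if early stoppage of the trial is needed due to unacceptable rates of drug related serious adverse events". Section 9.3.1 classes any death as a serious adverse event, and section 9.3.3 requires such events to reach the DSMC coordinator within 2 working days. Section 16.0 says the DSMC "reviews all local serious adverse events and unanticipated problems in real time as they are reported". No interim analysis is planned.

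Section 6.6 also has dose-limiting toxicity (DLT) rules for phase Ib. Two or more in cohort 1 stop the phase I component with no phase II. Two in cohort 2 or 3 lower the dose.

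**The concern.** A mandatory safety rule should not become more lenient as outcomes get worse. Under this wording, replacing one of two prolonged grade 4 events with a treatment-related death removes the automatic stop. Separate counts also do not aggregate across grades, which is the purpose the rule states for itself. The documents give no reason for treating the mixed pair differently.

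At stake is whether patients go on being entered after a related death and a prolonged life-threatening event because nobody was obliged to close enrolment. The gap matters most after cycle 1 and throughout phase II, where no other numeric safety rule applies.

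**Working it through.** The plan states no operating characteristics for this rule, so there is no figure to reproduce.

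**Step 1: the logic, which needs no assumption.** Let a be the number of qualifying grade 5 events and b the number of qualifying grade 4 events. As written, entry closes if a ≥ 2 or b ≥ 2. A pooled rule would close entry if a + b ≥ 2.

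| a | b | As written | Pooled |
|---|---|---|---|
| 0 | 2 | closes | closes |
| 2 | 0 | closes | closes |
| 1 | 1 | stays open | closes |
| 1 | 2 | closes | closes |
| 2 | 1 | closes | closes |

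The only difference is at (1,1). From there a third qualifying event of either grade triggers the written rule, so the automatic stop comes one event late, or never if no third event occurs.

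**Step 2: number of patients.** Section 6.6 says "Cohort 1 has been expanded to 6 patients". Cohorts 2 and 3 take 3 to 6 each. Section 12.1 puts 40 in phase II, and 6.6 says patients at the MTD "represent the first three patients accrued to the phase II aspect". If all cohorts fill, n = 6 + (3 to 6) + (3 to 6) + 40 − 3 = 49 to 55. Patients who have TACE only and are replaced are not counted.

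**Step 3: trigger probabilities.** The documents give no rate for these events. Assume a proportion p of patients have one qualifying event each and a fraction q of those events are fatal. With N ~ Binomial(n, p):

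- pooled = P(N ≥ 2)
- gap = P(N = 2) × 2q(1 − q)
- as written = pooled − gap

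For q = 0.20, 2q(1 − q) = 0.32:

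| n | p | P(N = 2) | Pooled | As written | Gap |
|---|---|---|---|---|---|
| 49 | 2% | 0.1820 | 0.2568 | 0.1986 | 0.0582 |
| 49 | 5% | 0.2638 | 0.7101 | 0.6257 | 0.0844 |
| 49 | 10% | 0.0831 | 0.9631 | 0.9365 | 0.0266 |
| 55 | 2% | 0.2036 | 0.3013 | 0.2362 | 0.0652 |
| 55 | 5% | 0.2449 | 0.7681 | 0.6897 | 0.0784 |
| 55 | 10% | 0.0558 | 0.9784 | 0.9605 | 0.0179 |

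For q from 0.10 to 0.50 the gap is 3.3 to 10.2 points at 2%, 4.4 to 13.2 at 5% and 1.0 to 4.2 at 10%.

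**Step 4: how often the written rule catches up.** Among trials whose first two qualifying events are one of each grade, the share reaching a third is 1 − P(N = 2)/P(N ≥ 2). This is 29–32% at 2%, 63–68% at 5% and 91–94% at 10%.

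**Step 5: what the gap leaves out.**

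- *Timing.* The rule only closes entry, so a second event after the last patient has entered changes nothing. I simulated uniform entry over the 24 months in section 12.1, with an assumed exponential time from entry to event. The second event comes before the last entry in about 88%, 66% and 44% of one-plus-one trials for mean times of 1, 4 and 8 months. At n = 49 and p = 5%, 8.4 points becomes 8.4 × 0.88 = 7.4, 8.4 × 0.66 = 5.5 or 8.4 × 0.44 = 3.7.
- *Earlier closure.* Trials that pass through (1,1) and reach a third event close under both rules, but sooner under the pooled one. Their share is 0.32 × P(N ≥ 2) − gap. At n = 49 and p = 5% that is 0.32 × 0.7101 − 0.0844 = 0.143.
- *Repeat events.* If a share r of non-fatal cases has two prolonged grade 4 events, the gap is multiplied by (1 − r). At 5% it becomes 6.3 to 5.9 points for r = 0.25 and 4.2 to 3.9 for r = 0.50. Section 1.6 makes overlapping cytopenias plausible, but its figures pool grades 3 and 4, concern another drug of the class and give no durations. They do not determine r.

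**The case against.** The strongest reply is that a death plus a prolonged grade 4 event cannot go unreviewed. Every death is reported as a serious event, and under section 9.3.3 "The DSMC Chairperson determines whether action is required and either takes action immediately", calls a special session or defers to a scheduled meeting. Section 16.0 adds weekly phase I meetings with real-time toxicity review, and disease-team review in phase II. This stands, and it limits the consequence. It does not repair the rule: the protocol puts a mandatory trigger on top of that same oversight, and the discretion includes deferral to a committee that meets quarterly.

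A reader might infer that the protocol requires enrolment to continue in the one-plus-one case. It does not; it only fails to require closure. A reader might also infer that nothing but judgement applies in that case anywhere in the study. That is too broad. If both events are first-cycle DLTs related to LEE011 in two patients at the same dose level, cohort 1 stops with no phase II, and cohorts 2 and 3 lower the dose. Those rules do not reach events after cycle 1, events attributed to TACE alone, or phase II.

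The last objection is that strictness is a judgement. At an assumed 5% rate the written rule already triggers in 63–69% of trials, events only possibly related count, and no document calls 5% unacceptable. That is fair as an argument about the threshold, but it does not justify ranking the worse pair below the milder one.

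**Conclusion.** The point holds in a narrow form. The mandatory rule reverses the order of severity for one tally, exactly one related grade 5 event and one related grade 4 event lasting at least 7 days. This follows from the wording alone. Outside the phase Ib DLT exception, stopping in that case rests on the DSMB (9.4) or DSMC (9.3.3, 16.0) until a third qualifying event.

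The size rests on assumed rates. With n = 49 to 55 and q = 0.20, pooling raises the final trigger probability by 5.8–6.5 points at 2%, 7.8–8.4 at 5% and 1.8–2.7 at 10%. These figures should not be read as a measure of harm. They are upper bounds on the share of trials in which only the pooled rule would close entry, because some second events come after accrual ends. They do not count trials that would close under both rules but earlier under pooling. Discretionary stops and DLT stops are not modelled. This is a cheap improvement to consider, not a serious failure of safety monitoring.

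**What to change.** Use one sentence in both 6.6 and 9.4: *enrolment closes after any 2 events that are grade 5, or grade 4 lasting at least 7 days, in any combination, at least possibly related to study treatment; a grade 4 event that leads to death counts once, as grade 5.* The last clause settles something the documents leave open.

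If the mixed pair is left to judgement on purpose, say so in 9.4 and give the reason.

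The change is one sentence in two places, applied by the existing committee, with no new data and no change in sample size. The cost is more frequent early closure, possibly at rates the investigators would accept: from 0.20–0.24 to 0.26–0.30 at an assumed 2% rate, 0.63–0.69 to 0.71–0.77 at 5%, and 0.94–0.96 to 0.96–0.98 at 10%.

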6.2 STUDY TREATMENT

For this study, the term “investigational drug” refers to Novartis study drug LEE011. The procedure, chemoembolization, is standard of care for locally, advanced, non-metastatic HCC. Study treatment in this study refers to the combination of chemoembolization and LEE011.

LEE011 will be supplied by Novartis or its designee as 200 mg hard gelatin capsules as individual patient supply packaged in bottles. Storage conditions are described in the medication label. Chemoembolization will be performed in usual standard of care practice by the interventional radiology division at UT Southwestern Medical Center as described in section 6.12 .

All dosages prescribed and dispensed to the patient, and all dose changes during the study will be recorded in the drug accountability records.

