6.12.7 Subsequent Chemoembolizations

To proceed with subsequent chemoembolization, study subjects must meet the following criteria:

- \leq Grade 2 hematologic toxicity with the exception of:
 - serum creatinine $\leq 1.5 \text{ mg/dl}$;
 - serum bilirubin $\leq 3.0 \text{ mg/dl}$.

Repeat Chemoembolization (for either ipsilateral or contralateral disease) if indicated, should be performed at least 4 weeks apart. Up to 4 chemoembolizations can be performed in 6 months of the first chemoembolization. Additional chemoembolizations, if clinically indicated can occur after the first 6 months

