7.4 POST – TREATMENT FOLLOW-UP PHASE

7.4.1 End of Treatment and Early Withdrawal Visit

Patients who completely discontinue study treatment should be scheduled for an End of Treatment (EOT) visit within 15 days following the last dose date of LEE011, at which time all of the assessments listed for the EOT visit will be performed. For details of the assessment, see Table 7-1.

At a minimum, all patients who discontinue study treatment, including those who refuse to return for a final visit, will be contacted for AE evaluations during the 30 days following the last dose date of LEE011.

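### The study-wide stopping rule counts related grade 4 and 5 events only while the patient is on study treatment, so a related event that begins after permanent discontinuation is left to discretionary review

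*Combined protocol and SAP*

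**What the plan says.** The rule appears twice. Section 9.4 (Stopping rules) ends entry once there are two grade 5 events, or two grade 4 events lasting at least 7 days, that "occur while at patient is receiving study treatment and the adverse events are attributed" to study treatment as definitely, probably or possibly related. Section 6.6 gives the same thresholds for events that "occur at any time while the patient is still receiving study treatment" and are "related to either LEE011 or TACE the study will be terminated to enrollment". Neither place gives a period after the last dose.

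The end of study treatment is not defined for this purpose:

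- Section 6.2: "Study treatment in this study refers to the combination of chemoembolization and LEE011".
- Section 6.12.7: "Additional chemoembolizations, if clinically indicated can occur after the first 6 months".
- Section 7.4.1 places the end-of-treatment visit "within 15 days following the last dose date of LEE011", so it ties the end of treatment to LEE011 alone.
- Section 6.6: "If a patient has a DLT that patient will not receive further LEE011".

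Other sections look beyond the last dose. Section 7.4.2 follows safety for 30 days after the last LEE011 dose, and section 3.1 records adverse events for up to 30 days after LEE011 stops (section 12.1 says up to a year after leaving the study). Section 9.5 covers events within 30 days of the last protocol treatment and also later events attributed to the agents.

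Oversight is separate from the count. Section 9.4 lets the DSMB stop the trial for unacceptable rates of drug-related serious events, with no on-treatment limit. Section 9.3.3 sends local serious events to the DSMC coordinator within 2 working days.

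**The concern.** This is the plan's only numerical safety trigger that covers the whole study. The other counting rules, for dose-limiting toxicity, work within one dose cohort and one cycle. Its value is that two qualifying events stop entry without further judgement.

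Read literally, a related death or prolonged grade 4 event with onset after permanent discontinuation does not count. The protocol removes patients from LEE011 for severe toxicity: any dose-limiting toxicity in phase Ib, and most grade 4 reactions in Tables 6-4 to 6-7. The patients who leave the counting window thus include those who have already shown toxicity.

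Two borderline cases depend on the reader. A toxicity that begins on LEE011 and becomes fatal after it stops can be read either way, because section 9.3.1 treats death as a grade of the same event. A patient who has stopped LEE011 but still receives chemoembolization is on study treatment by section 6.2 and off it by the dating in section 7.4.1.

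**Working it through.** The plan gives no operating characteristics for this rule, so there is no figure to reproduce. The check has a textual part and an illustrative part.

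**Which events count under the present wording**

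| Event (related) | Counted? |
|---|---|
| Grade 4, begins on treatment, lasts at least 7 days | Yes |
| Grade 4 or 5 during a rest week or dose hold | Not clearly off treatment |
| TACE-related grade 5 or prolonged grade 4 before LEE011 starts | Yes, reading 6.2 with 6.6 |
| Begins on LEE011, fatal after it stops | Unclear |
| New onset after LEE011 stops, TACE continuing | Unclear |
| New onset after all study treatment has stopped | No |

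**Size of the gap**

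*Patients on LEE011.* The study summary gives 9 to 18 in phase Ib and 40 in phase II. Section 6.6 carries three patients over. So n = 9 + 40 − 3 = 46 to 18 + 40 − 3 = 55.

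*Share of time at risk that lies after the last dose.* Assume exponential PFS, treatment until progression, and a constant event rate through a window w after the last dose. Then f = w / (mean + w), with mean = median / ln 2.

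- Historical median 8 months: mean 8 / 0.693 = 11.54 months.
- Target median 8 / 0.69 = 11.59 months: mean 16.73 months.
- 30-day window, w = 0.986 months: f = 0.986 / 12.53 = 7.9%, or 0.986 / 17.71 = 5.6%.
- Shorter window of five half-lives. Section 1.7.4.1 gives a mean effective half-life of 32.6 hours, so 5 × 32.6 / 24 = 6.8 days and w = 0.223 months: f = 0.223 / 11.76 = 1.9%, or 0.223 / 16.95 = 1.3%.

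*Grade 5 limb.* P(at least two countable deaths) is the binomial upper tail with n patients and rate p(1 − f). The related-death rates p are assumptions.

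| n | p | f = 0 | 1.3% | 1.9% | 5.6% | 7.9% |
|---|---|---|---|---|---|---|
| 46 | 2% | 0.2345 | 0.2301 | 0.2281 | 0.2157 | 0.2079 |
| 46 | 5% | 0.6768 | 0.6696 | 0.6664 | 0.6456 | 0.6320 |
| 55 | 2% | 0.3013 | 0.2960 | 0.2936 | 0.2786 | 0.2692 |
| 55 | 5% | 0.7681 | 0.7616 | 0.7587 | 0.7395 | 0.7268 |

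The loss is 1.9 to 4.5 percentage points with the 30-day window and about 0.5 to 1.0 points with five half-lives.

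*Whole rule.* 1 − P(X5 ≤ 1) × P(X4 ≤ 1), where X5 and X4 are the numbers of countable grade 5 and prolonged grade 4 events. Prolonged grade 4 events are assumed in 5% or 10% of patients, independent of deaths, with the same 7.9% share excluded from both limbs. The largest loss is at n = 46 with 2% deaths and 5% grade 4: 0.753 to 0.708, or 4.4 points. The smallest is at n = 55 with 5% and 10%: 0.995 to 0.991, or 0.4 points.

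**The case against.** The strongest reply is that an automatic trigger limited to on-treatment events, with later ones left to judgement, is a legitimate design choice, and that oversight already covers the gap. Local serious events reach the DSMC within 2 working days and its chair may act at once. Section 9.5 requires reporting of related events even after 30 days. Section 7.4.2 follows events that led to discontinuation until they resolve or stabilize. Nothing stops the DSMB from acting on two related deaths after treatment. This stands, and it is why the point is minor. It does not remove the point, because the discretionary route has no stated number or window.

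The figures are also soft. The event rates have no source in the documents, and risk may fade well before 30 days. The rule only stops entry, so a trigger after accrual closes protects few people, yet the calculation counts every patient over all treatment time. All of this stands.

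A reader might infer more than the documents support:

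- *That section 6.6 contradicts itself by saying at any time.* The phrase can be read as a contrast with the cycle 1 window for dose-limiting toxicity in the sentence before it. Section 9.4 does state a broad aim covering the whole study; that favours a wider window but does not show an error.
- *That severe toxicity leading to discontinuation escapes the count.* A grade 4 event that begins on treatment and lasts at least 7 days is counted.
- *That a quarter or half of events would be missed.* No document gives such a share.

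**Conclusion.** The point holds in a narrow form. On the literal wording of sections 6.6 and 9.4, a related grade 5 or prolonged grade 4 event with onset after permanent discontinuation is outside the automatic count, although the protocol already collects and reports events over that period. It is a worthwhile optional clarification and not a failure of oversight.

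The loss in the chance of triggering is roughly 0.5 to 4.5 percentage points for the grade 5 limb. For the whole rule it is 0.4 to 4.4 points when 7.9% of events are excluded, and less with a shorter window. These figures rest on assumed event rates, treatment to progression, and a constant rate for either 30 days or five half-lives after the last dose. The case for changing the text rests on clarity and low cost more than on these numbers.

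**What to change.** In both sections, replace the on-treatment condition with: *with onset from the first on-study chemoembolization to 30 days after the last dose of LEE011 or the last on-study chemoembolization, whichever is later*. Add that an event's duration and any fatal outcome count even if they occur after treatment has stopped. Event counts and grade thresholds do not change.

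The window should not begin at the first LEE011 dose, and the count should not be limited to patients who have started LEE011. Either would drop TACE-related deaths and prolonged grade 4 events in eligible patients who never meet the LEE011 starting criteria within 28 days (section 6.12), which the present wording covers. Section 6.6 records that TACE-related toxicity has already led to changed criteria for cohort 1. Patients removed as RB-negative screen failures (Table 7.1, note 7) may be left to DSMC review if the text says so.

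The cost is a short amendment. Section 7.4.2 dates its 30 days from the last LEE011 dose, so it should also run 30 days from the last on-study chemoembolization where that is later. Table 7.1, note 2 already schedules examinations and laboratory tests every other week for two cycles after each procedure, so little extra data collection is needed. The downside is that the termination rule may be reached slightly sooner, by roughly 0.5 to 4.5 points under the assumed rates.
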